### **13.2 Recruitment procedures (Aim 2 Debrief Interviews)**

*All interviewees will be recruited after their involvement in Aim 1 activities to eliminate the possible impact of the interview on outcomes.*

**13.2.1 Patients:** We will recruit a purposive sample of patient-participants who completed research activities in Aim 1 based on audio recording use and health literacy. At T2 follow up, the RA will assess the participant's interest in taking part in an interview about their experience with audio recordings. A list of patients who are interested will be compiled, from which we will identify patients to interview stratified by recording use and health literacy.

We will use the generated lists to identify potential patient interviewees. We will call by telephone or send a letter informing them that they have been selected for an interview. If a letter is sent, it will be followed by a telephone call to confirm interest and arrange a time and place to conduct the interview (Appendix 13. Patient Interview Guide). People interested in participating will meet with the research assistant at the clinic, office, or by telephone or videoconference to complete (Appendix 13b Patient Consent Form)

**13.2.2 Caregivers:** During telephone calls to patients from the AUDIO group, the RA will also explain that we would like to conduct interviews with caregivers who have received or listened to recordings from the patient. If the patient is willing to share the contact information of a caregiver (family member, friend) we will then contact them by a telephone call. We will inform the caregiver that the patient has given us permission to contact them about their experience using the recording. We will generate a list of interested caregivers stratified by recording use.

PROTOCOL TITLE: *The impact of sharing audio recorded clinic visits on self-management in older adults: a multisite trial*

For caregivers, we will use the generated lists to identify potential interviewees. We will send a letter informing them that they have been selected for an interview, followed by a telephone call to confirm interest and arrange a time and place to conduct the interview (Appendix 14. Caregiver Interview Guide). People interested in participating will meet with the research assistant at the clinic, office, or by telephone or videoconference to complete (Appendix 14b. Caregiver Consent Form). A follow up call will be conducted with all caregivers who took part in an interview in order to obtain demographic information (Appendix 33. Caregiver Demographic Script).

**13.2.3 Clinical staff:** Clinical staff who took part in the project will be contacted by email by the site RA and invited to take part in an interview at a time convenient to them. Interested clinicians will meet with RA to complete informed consent. In all instances, participants will be offered a \$30 honorarium for taking part in an interview.

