## 2.0 Objectives\*

**Aim 1. Conduct a multi-site, two-arm, parallel group, patient-randomized, blocked, controlled, pilot trial with 3-month follow up, to determine the feasibility and acceptability of sharing audio recordings of clinic visits (AUDIO) on self-management in older adults with diabetes and hypertension, compared to the after visit written summary (AVS) alone (Usual Care/UC).** We will determine:

- 1.1 *Feasibility* of a larger trial by meeting recruitment targets at each site (n=30 patients and 6 clinicians per site; total N=108) and determining the optimal strategy to achieve a high retention rate and adherence to the study protocol.
- 1.2 *Acceptability* by assessing the proportion of patients and clinicians who agree to take part in the project and the proportion of patients who listen to the recording.
- 1.3 *Potential effectiveness* by collecting data on the impact of audio recordings on patient experience, understanding, self-management and clinician behavior. *We will explore our main hypothesis that compared to those receiving UC, patients randomized to also receive audio recordings (AUDIO) of clinic visits will report greater self-management (Patient Activation Measure – Short Form) at 3 months. We will also explore whether the effect of AUDIO on self- management compared to UC is greater for patients with low health literacy than those with high health literacy.*

**Aim 2. Assess the acceptability of study protocol and the use of audio recording of visits as part of care** by conducting semi-structured interviews with participating clinicians, patients and caregivers (i.e. person involved in the patient's care, including a family member, friend or formal caregiver).

We hypothesize that this multisite trial will be highly feasible and that recording and sharing of clinic visits will be highly acceptable.

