### **10.2 Inclusion / Exclusion Criteria (Aim 2 Debrief Interviews)**

#### **10.2.1 Inclusion/Exclusion Criteria (Aim 2)**

*Patients:* We will recruit a purposive sample of patient-participants from Aim 1 based on recording use (listened to none, one or all recordings; shared recording or not) and health literacy [SAHL-E score  $\leq 14$  (low health literacy) or  $> 14$  (high health literacy)].

PROTOCOL TITLE: *The impact of sharing audio recorded clinic visits on self-management in older adults: a multisite trial*

**Caregivers:** Patients will identify family members / caregivers who are 1)  $\geq 18$  years of age, 2) who can communicate in English or Spanish; and 3) have received access to the patient's audio recordings.

**Clinic staff:** We will include healthcare professionals and administrators who have been involved in the trial at each site including MDs, NPs, Nursing Staff, Medical Assistants, and Administrators.

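### Aim 2 patient interviews are drawn only from Aim 1 completers asked at T2, so patients who withdrew or missed T2 are absent from the interviews meant to judge the acceptability of the protocol

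*Combined protocol and SAP*

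**What the plan says.** Section 13.2.1 sets out how patients reach an Aim 2 interview, in three steps:

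- The frame: "We will recruit a purposive sample of patient-participants who completed research activities in Aim 1", with recording use and health literacy as the sampling factors.
- The timing: "At T2 follow up, the RA will assess the participant's interest in taking part in an interview about their experience with audio recordings".
- The selection: "A list of patients who are interested will be compiled, from which we will identify patients to interview stratified by recording use and health literacy".

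Section 10.2.1, which gives the Aim 2 eligibility criteria, is wider: "We will recruit a purposive sample of patient-participants from Aim 1 based on recording use", together with health literacy. It states no completion condition, and it names no stratum for patients who left the trial.

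Section 2.0 gives Aim 2 two objects: whether the study protocol is acceptable, and whether recording is acceptable as part of care. Section 6.8 plans six patient interviews per site. Section 4.1 places the Acceptability of Intervention Measure (AIM) and the Feasibility of Intervention Measure (FIM) in the three-month assessment.

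For patients who leave, the plan records a reason: on the withdrawal form (Section 14.0), when a patient who could not be reached by telephone is approached in clinic (Section 6.2), and in the loss-to-follow-up records (Sections 17.1.1, 17.1.7 and 18.0).

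**The concern.** This is a feasibility pilot, and its qualitative arm is there to explain how patients experienced the protocol as well as the recordings. A patient who withdrew or missed T2 fails all three steps in Section 13.2.1, and no other section clearly opens another route. The same patients supply no AIM or FIM score. Both patient sources that describe acceptability in any depth therefore come from people who stayed.

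If some patients leave because visits, surveys or contact attempts were burdensome, the interviews would under-represent that view. The larger trial could then be planned on an account of the protocol that is kinder than the one all enrolled patients would give. Aim 1.1 also speaks of "determining the optimal strategy to achieve a high retention rate and adherence to the study protocol", and patients who were not retained would have something to add to that.

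**Working it through.** **1. The plan's own figures.** Inputs: three sites with 30 patients and 6 clinicians each (Sections 12.0 and 26.0); six patients, six caregivers and six clinicians interviewed per site (Section 6.8).

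- Aim 1: 3 × (30 + 6) = 108, of whom 3 × 30 = 90 are patients. This agrees with the plan.
- Aim 2: 3 × (6 + 6 + 6) = 54, of whom 3 × 6 = 18 are patients. This agrees with the plan.

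**2. Who is outside the interview frame.** Number outside = 90 × (1 − retention at T2).

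- At about 30% attrition, the rate reported for the team's earlier pilot in cardiology inpatients (Section 3.2.5): 90 × 0.30 = 27, or 9 per site.
- With the Section 4.1 target met: it requires more than 0.70 × 90 = 63 patients, so at least 64 retained and at most 90 − 64 = 26 lost.
- Under assumed attrition of 10% and 20%: 9 and 18 patients.

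**3. A benchmark for scale.** Suppose 18 patients were drawn at random from all 90, of whom k did not complete. The expected number of non-completers is 18 × k / 90. The chance of drawing none is C(90 − k, 18) / C(90, 18).

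| Assumed attrition | k | Expected among 18 | Chance of none |
|---|---|---|---|
| 10% | 9 | 1.8 | 0.12 |
| 20% | 18 | 3.6 | 0.011 |
| 30% | 27 | 5.4 | 0.0007 |

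Under Section 13.2.1 the number is 0 by rule. The plan samples purposively, so the table shows only what the rule removes; it is not a standard that the interviews have to meet.

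**4. Whether the stated reason for the timing requires completion.** Section 13.2 recruits interviewees only after their part in Aim 1 is over, so that the interview cannot influence outcomes. A patient who has withdrawn, or whose T2 window has closed without an assessment, has no further Aim 1 outcome survey to influence. The reason given supports interviewing late. It does not support interviewing completers only.

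**The case against.** The strongest reply is that patients who disengage are not silent in this plan. Reasons for withdrawal and loss are recorded, reported to the site PI, and discussed at weekly meetings where mitigation is considered (Section 18.0). Patients who do not follow the listening regime are contacted outside the standard assessments (Section 17.1.2). Section 10.2.1 deliberately seeks patients who listened to no recording and patients with low health literacy, so people who rejected the intervention but reached T2 are sampled. Clinicians and caregivers are interviewed too.

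Much of this stands, and it rules out three stronger readings:

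- *That patients who left cannot be heard at all, or that the retention question has no information from them.* A reader might infer this, but the documents do not support it. Retention belongs to Aim 1.1, which has its own monitoring. The gap concerns the semi-structured interviews and the T2 scales.
- *That the interviews will overstate acceptability.* Nothing in the documents measures the direction or size. Some losses carry no objection to the protocol, or leave nobody to interview: death or change of provider (Section 18.0), disease progression or a newly met exclusion criterion (Section 14.0), cognitive decline or administrative removal (Section 15.0).
- *That Sections 10.2.1 and 13.2.1 contradict each other.* The second narrows the first, and the completion phrase may have been meant only as a rule on sequence.

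What does not stand is that these channels replace the interview. A recorded reason is not a 20- to 30-minute conversation about the protocol. The contact with non-listeners concerns delivery of the intervention. The provision in Section 6.8 for meeting patients who cannot be telephoned sits within the interview procedures and does not clearly cover someone who never joined the T2 list.

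**Conclusion.** The point holds in a limited form. As written, no patient who withdrew or missed T2 can be interviewed, and the same patients supply no AIM or FIM score. The patient findings on the acceptability of the protocol may lean toward those who found it tolerable.

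The group outside the frame is 27 of 90 if attrition matches the earlier pilot, and at most 26 if the retention target is met. Both figures assume 90 patients are enrolled and count every patient without T2, including those who died, became ineligible or could not be found. The number who could realistically be interviewed is smaller and unknown. The figure of 27 also assumes that attrition in a cardiology inpatient pilot carries over to primary care.

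This is an inexpensive improvement to a small qualitative component. No sample size, error rate or feasibility threshold changes.

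**What to change.** 1. In Section 13.2.1, replace the completion condition with wording such as *whose involvement in Aim 1 has ended*. This keeps the sequence rule and brings the section into line with Section 10.2.1.
2. Ask about interest in an interview at T2 and also at contacts that already exist: when the withdrawal form is completed, and when a patient who could not be reached is approached in clinic under Section 6.2. Contact later only those who agree. Both steps are needed, because changing the wording alone would leave the T2 question as the only way in.
3. Hold one of the six patient interviews per site for a patient who withdrew or missed T2. If none agrees, give the place to a completer. The total stays at 18.
4. If no such patient is interviewed, state in the report that the patient interview findings come from completers only. If the interviews are already done, this is the only step still open.

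The cost is a small IRB wording change and up to one fewer completer interview per site, in a sample already spread over listening level, sharing and health literacy. The gain is at most three interviews, and patients who never respond to any contact will still be missed. The withdrawal form (Appendix 15) is not among the documents reviewed, so the sponsor should first check what it already asks.

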## **14.0 Withdrawal of Subjects\***

Any participant can discontinue participation at any time. An investigator may also discontinue or withdraw a participant from the study for the following reasons: 1) disease progression which requires discontinuation of the study intervention, or 2) if the participant meets an exclusion criterion (either newly developed or not previously recognized) that precludes further study participation. The reason for participant discontinuation or withdrawal from the study in either case will be recorded on the Participant Withdrawal Case Report Form (Appendix 15. Participant Withdrawal Form).

## **15.0 Risks to Subjects\***

The risks associated with participation in the project activities are deemed to be low and are outweighed by the potential benefits. Before data collection starts, all study personnel will be required to undertake appropriate CITI coursework, including, but not limited to, HIPAA training and Good Clinical Practice. The MPIs and research staff will meet weekly by teleconference, from the time of study award, to plan protocol implementation at each site. In month six, a two-day 'kick off' training event will be hosted at Dartmouth College, and all study team members will join in person and/or virtually. During this training event, we will review and train research coordinators and assistants in all aspects of the study protocol including identification of patients, screening administration, recruitment and consent, survey administration and follow-up calls/emails and plans for unexpected events. Additionally, patient recruitment will not begin until the clinical trials office at each site approves the study binder containing IRB approved protocol, surveys, protocol checklists, staff training and CITI certifications, and the trial is registered on ClinicalTrials.gov. The following sections provide a detailed overview of our specific efforts to minimize risks including risks to privacy and

PROTOCOL TITLE: *The impact of sharing audio recorded clinic visits on self-management in older adults: a multisite trial*  
confidentiality:

1. Information on eligible patients collected at each study site prior to consent will only be shared with Collaborative Institutional Training Initiative (CITI)-trained researchers from Dartmouth College, UTMB Health and VUMC, and will be stored securely on the HIPAA-compliant REDCap database. Names and contact details of patients who decline to take part in the study will be stored until recruitment is completed, to ensure the patient is not contacted to take part again. Following the completion of recruitment, we will immediately delete their information from the database.
2. We have consulted with research and privacy officers who have approved our proposed research, including the recording and sharing of clinic visits with patients. Patients will provide written consent for our research team to maintain a copy of all recorded clinic visits. The storage of all patient information collected for this project, including audio-recordings will be stored in HIPAA-compliant server (audio recordings), and REDCap database (all study data and audio recordings) housed in the Geisel School of Medicine, Dartmouth College. An additional copy of the study data and audio recordings may be housed securely at each participating site.
3. Steps taken to reduce the possibility of recruiting individuals with significant cognitive deficits: 1) a trained research assistant will review the medical record – individuals meeting any exclusion criteria will not receive a telephone call; 2) a trained Research Coordinator will administer a cognitive assessment using the validated Six Item Screener of Cognitive Function (SIS); and 3) the clinician may choose to exclude a patient due to significant cognitive deficits. Should a clinician choose to exclude a participating patient due to the development of significant cognitive deficit (or one of the other exclusion criteria) during the 3-month follow up, we will document this and the patient will be thanked and informed both in person and by mail, that participation in the project is complete.
4. Both in-person and telehealth clinic visits in each primary care setting happen in a private room. We will place a sign on the door of the consultation room indicating a recording is currently taking place and that those who enter may be recorded (see Appendix 6. Recording Sign). At any time, the clinician or patient may choose to pause the recording. In the case a medical translator is needed to support the visit, this will be identified ahead of the patient visit by the RA. The translator will be informed that the patient is participating in a research project where the clinic visit is being recorded and their consent (written or verbal) will be sought. This strategy has been used successfully at UTMB where visits at the cancer clinics are audio recorded and in our recently completed pilot

PROTOCOL TITLE: *The impact of sharing audio recorded clinic visits on self-management in older adults: a multisite trial*

trial at Dartmouth Hitchcock Medical Center, Heart Sounds. In the unlikely situation that a translator is uncomfortable, a new translator for the patient will be sought prior to the visit.

5. It is extremely unlikely that an audio recording will be posted to social media or used as part of legal proceedings. Such events have not been documented during our previous studies. However, should either event occur we will follow these processes:

Social media post. While the study team is not monitoring participants' social media, in the event that the study team are informed that a patient has 'posted' an audio-recording created for the proposed study on a social media website the patient will be asked to remove the post by the study team. We will also inform our IRB, risk management at the clinic site and the participating clinician. Refusal to remove the recording from social media may result in the participant's administrative removal from the study.

Legal proceeding. Should the study team be informed that a recording has become part of the legal proceeding, we will also inform our IRB, risk management at the clinic site and the participating clinician. This would lead to administrative removal of the participant from the study

6. Patients who have consented to take part in the study will be assigned a unique study identification number. All data collected from participants will be identified only by these study identification numbers. This will minimize risks regarding breach of confidentiality with respect to the study data. The link between each study identification number and participant name will be kept in a password-protected file on a password protected computer.

7. Printed forms with identifiable patient data, e.g. signed consent forms and medical releases of information, will be stored in separate file folders in locked filing cabinets at the offices of the project coordinator of each clinicsite.

8. All digital data, including audio-recordings (clinic visits and debrief interviews), will be stored in secure, password-protected computer files on a password-protected computer, or in a HIPAA-compliant database.

9. No medical records or protected health information shall be re-disclosed, unless required by law.

10. De-identified data will be stored in the Dartmouth Dataverse, and available, upon request, to the broader research community and appropriate IRB approval; approval to use data in for this purpose will be included in the consent forms.

11. The entire research team will complete confidentiality training.

PROTOCOL TITLE: *The impact of sharing audio recorded clinic visits on self-management in older adults: a multisite trial*

## 16.0 Potential Benefits to Subjects\*

Participants who are randomly assigned to the AUDIO arm will have immediate post-visit access to audio-recordings of their clinical visits, evidence suggests such access may enhance understanding and recall of health care information. We hypothesize that patient will also be better able to manage their health due to recording access. While patients in the control group will not receive a recording, they will benefit from knowing that findings from this research may benefit future patients like themselves. The inclusion of older adult patients with a complex condition, who are often excluded from trials, is also a benefit, as patients may enjoy the opportunity to take part in research. As such, we believe the risks to research participants about potential loss of confidential information, which we will take rigorous precautions to avoid (see Protection Against Risks), are outweighed by the potential benefits of improved clinical outcomes through informing healthcare delivery practices aimed to support better self-management, and satisfaction with care, for both participants and the larger population of older adults with diabetes, hypertension, and complex multimorbid conditions more broadly.

## 17.0 Data Analysis, Management and Confidentiality

### 17.1 Data analysis plan (Aim 1 Trial)

Pilot studies can serve many purposes. Our pilot project is principally designed to determine the feasibility of implementing our proposed trial protocol and the acceptability of the AUDIO intervention. We will focus on the feasibility of study processes, resources, and study management, concurrent adaptations to the trial protocol as needed. We will review data weekly, and determine the need to make adjustments to the trial (in accordance with the current IRB policies regarding amendments to protocols). We will also gather preliminary data on the impact of the AUDIO intervention on: self- management ability at 3 months as measured by the Patient Activation Measure-Short Form (PAM-SF), interpersonal processes of care in the visit (Interpersonal Processes of Care Scale), patient satisfaction (PSQ-18), treatment adherence (Medical Outcomes Study, General Adherence survey; ARMS-7), physical and mental functioning (PROMIS 10), quality of life (EURO-QOL), quality of diabetes and hypertension care (EMR abstraction), number of clinic contacts e.g., phone calls, patient portal messages (EMR abstraction), ER visits (EMR abstraction) and hospitalizations (EMR abstraction). We will also explore whether the impact of audio recording is greater for individuals at highest risk of poor self-management including those with low health literacy (Short Assessment of Health Literacy), moderate to severe depression (PHQ-8) or anxiety (GAD-7), high perceived stigma and high disease burden (Charlson Co-Morbidity Index), or by patient sex, race or ethnicity. As such our analysis consists principally of descriptive statistics.

